**STUDY SCHEMA**

**STUDY SYNOPSIS**

Title	Phase Ib/II Trial of Interleukin-2 and PD-1 Checkpoint Inhibitor, Nivolumab In Metastatic Clear Cell Renal Cell Cancer
Phase	Phase Ib/II
Methodology	
Single arm, multi-site phase Ib/II clinical trial of standard doses of High Dose Interleukin-2 (HD IL2) (600,000 IU/kg/dose intravenously during two 5-day cycles 9 days apart) in IL-2 eligible clear cell metastatic RCC subjects in combination with Nivolumab.
 
Nivolumab will be administered intravenously at 480 mg/dose over 60 minutes every 28 days, starting 1 week to 3 weeks after the start date of the first cycle of IL2 and continued for up to 48 weeks total in the absence of disease progression by RECIST 1.1 criteria, unacceptable toxicity, withdrawal of consent or lack of clinical benefit as determined by the PI.
 
Nivolumab may be continued beyond 48 weeks off-study at the discretion of the investigator at his or her clinical judgment.
 
Initially 10 patients will be enrolled in the phase 1b portion of the study.
 
The first 3 patients will be treated with sequential (rather than interspersed) treatment. They will receive 2 cycles of HD-IL2 given in standard fashion (two 5-day cycles one week apart) followed by nivolumab starting the week after the second IL-2 cycle and continuing every 4 weeks as per standard nivolumab dosing.
 
We will perform a safety analysis after the first 3 patients are treated. If 2 out of 3 of the first patients suffer a grade 3 or 4 immune related toxicity, the study will stop. The 4th patient will not be enrolled until after the analysis of the 3 patient cohort is complete and submitted to the regulatory bodies.
 
If <2 patients suffer a grade 3 or 4 immune related toxicity, the study will enroll up to 7 more patients treated with Nivolumab administered intravenously at 480 mg/dose over 60 minutes every 28 days, starting 1 to 3 weeks after the start date of the first cycle of IL2. We will monitor these patients continuously for immune mediated dose limiting toxicities for 28 days from the first dose of nivolumab. If, at any time during accrual to the phase1 b portion, 6 patients or more have a grade 3 or 4 immune mediated event of interest (as described in section 5.2.1) we will pause the study and modify/discontinue the protocol in consultation with the site principal investigators and applicable regulatory authorities. If ≤ 5 of the 10 patients have a grade 3 or 4 immune mediated event of interest (as described in section 5.2.1), we will proceed to the phase II portion of the study. Please note: immune mediated events of interest do not include those that are known to occur during high dose IL-2 monotherapy and are reversible by holding IL2 dose(s) such as capillary leak syndrome.

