
Statistical Methodology
	
This is a single arm phase Ib/II trial of Nivolumab and IL-2 in patients with Renal Cell Carcinoma. The phase Ib has an endpoint of safety and the phase II primary endpoint is overall response rate (ORR = CR or PR) at 12 weeks. A recently reported trial of Nivolumab after 1 prior therapy in RCC reported had an ORR of 25%. With the addition of IL-2 treatment to nivolumab, we hypothesize an ORR of approximately 46% in this population.
 
Study Design/Study Endpoints/Sample Size and Accrual  For the phase Ib portion of the study: We will accrue an initial cohort of 3 patients who will be treated with sequential (rather than interspersed) treatment. They will receive 2 cycles of HD-IL2 given in standard fashion (two 5-day cycles one week apart) followed by nivolumab starting the week after the second IL-2 cycle and continuing every weeks as per standard nivolumab dosing. If 2 out of 3 of the first patients suffer a grade 3 or 4 immune related toxicity of interest (see 5.2.1) the study will stop. The 4th patient will not be enrolled until after the analysis of the 3 patient cohort is complete and submitted to the regulatory bodies.
 
If <2 patients suffer a grade 3 or 4 immune related toxicity in the cohort of 3 patients, the study will enroll 7 more patients treated with Nivolumab administered intravenously at 480 mg/dose over 60 minutes every 28 days, starting 1 week to 3 weeks after the start date of the first cycle of IL2. We will monitor these patients continuously for immune mediated dose limiting toxicities for 28 days from the first dose of nivolumab with DLTs being reported as they occur. 10 total patients will be treated and observed for toxicity for 28 days from the first dose of Nivolumab. If, at any time during accrual, 6 patients or more have a grade 3 or 4 immune mediated event of interest (as described in section 5.2.1) we will pause the study and modify/discontinue the protocol in consultation with the site principal investigators and applicable regulatory authorities. If 5 or fewer patients experience grade 3 or 4 immune mediated toxicity of interest (see 5.2.1) during the toxicity window, then the study will continue to the phase II portion. We choose to examine toxicity after 10 patients because if 6 patients or more are found to have a DLT then the 95% exact binomial confidence interval will be > 25% and be indicative that there is too high an incidence of serious immune mediated toxicities.
 
The phase II portion of the trial will be a Simon mini-max 2-stage design. The first stage will accrue 12 patients (INCLUDING any evaluable patients accrued in the phase 1b portion). If more than 2 patients have a response (CR or PR) out of the 12 patients, then we will accrue 11 more patients for a total sample size of 23 evaluable patients. If more than 8 responses (CR or PR) are observed, then we will recommend further study of the combination. This design has 80% power and 10% type I error. If the true ORR of the combined treatment is 25% or less, the probability of early termination of the trial is 39%. If the true ORR is 46% or greater, then the probability of stopping early is only 3.6%. Patients accrued in the Phase Ib portion of the trial will also be included in the Phase II if they are evaluable as defined below.
 
Evaluable Patients: All patients who receive at least 1 dose of IL-2 and at least 1 dose of Nivolumab will be evaluable for the primary endpoint of overall response proportion in the phase II portion of the

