### **8.8 Stopping Rules**

Please refer to Section 11.1.

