#### 11.1 Study Design/Study Endpoints/Sample Size and Accrual

For the phase 1b portion of the study: We will accrue an initial cohort of 3 patients who will be treated with sequential (rather than interspersed) treatment as follows: they will receive 2 cycles of HD-IL2 given in standard fashion (two 5-day cycles one week apart) followed by nivolumab starting the week after the second IL-2 cycle and continuing every 4 weeks as per standard nivolumab dosing. If 2 or more out of 3 of the first patients suffer a grade 3 or 4 immune related toxicity of interest (see 5.2.1) **within 28 days** from the first dose of nivolumab (**DLT period**) the study will stop. The 4th patient will not be enrolled until after the analysis of the 3 patient cohort is complete and submitted to the regulatory bodies.

If <2 patients suffer a grade 3 or 4 immune related toxicity in the cohort of 3 patients, the study will enroll 7 more patients treated with Nivolumab administered intravenously at 480 mg/dose over 60 minutes every 28 days, starting 1 to 3 weeks after the start date of the first cycle of IL2. We will monitor these patients **continuously** for immune mediated dose limiting toxicities **for 28 days** from the first dose of nivolumab (**DLT period**). Up to 10 total patients will be treated and observed for toxicity for 28 days from the first dose of Nivolumab in the phase 1b portion.

If, at any time during accrual to the phase 1 b portion, 6 patients or more have a grade 3 or 4 immune mediated event of interest (as described in section 5.2.1) we will pause the study and modify/discontinue the protocol in consultation with the site principal investigators and applicable regulatory authorities. If 5 or fewer patients experience grade 3 or 4 immune mediated toxicity of interest (see 5.2.1) during the toxicity window, then the study will continue to the phase II portion.

We choose to examine toxicity after 10 patients because if 6 patients or more are found to have a DLT then the 95% exact binomial confidence interval (26% - 88%) will be > 25% and be indicative that immune mediated toxicity with this regimen is too great.

Dose-Limiting Toxicity is defined as a grade 3 or 4 immune mediated event of interest (as listed and described in section 5.2.1). Please note: immune mediated events of interest do not include those that might occur during high dose IL-2 and are reversible.

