## 11.2 Data Analyses Plans

Primary Endpoint Analysis:

Phase 1b: DLT count and proportion will be reported. Type, grade and attribution will be described by body system in the first 10 DLT evaluable patients. Number of IL-2 cycles and doses and Nivolumab doses will be summarized.

Phase II: Overall response rate at 12 weeks will be reported with the sample size and proportion of evaluable patients and the corresponding 95% exact binomial confidence interval.

Secondary Endpoint Analyses:

Safety will be defined by frequency of drug-related grade 3-5 adverse events including adverse events of interest within the duration of protocol, specified therapy and an additional 60 days following the last dose with the combination of HD IL2 and nivolumab, as assessed by NCI's CTCAE version 4.0. Counts and frequencies will be reported by body system, type and grade. Cycles and of each drug and doses/cycle of IL-2 will be described using descriptive statistics.

Survival endpoints are 24-month Overall Survival (OS) and 24-month Progression-Free Survival (PFS) as assessed by RECIST 1.1 criteria in subjects treated with the combination. Product-limit estimates from Kaplan-Meier methods will be used to report the 24-month OS and PFS proportions with 95% confidence intervals. Kaplan-Meier figures will be produced.

Interim Analysis for efficacy: An interim analysis for efficacy is planned after 12 response evaluable patients have been enrolled (total in the phase I b/II portions). If 2 or less patients have a response at 12 weeks then the trial will terminate. .

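### Both study-level toxicity rules end with the 10 phase Ib patients, so patients 11 to 23 have no pre-specified toxicity boundary; the plan's own criterion can be carried forward at little cost

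*Combined protocol and SAP*

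**What the plan says.** Section 8.8, headed Stopping Rules, reads in full "Please refer to Section 11.1".

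Section 11.1 contains two study-level toxicity rules:

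- **First 3 patients.** "If 2 or more out of 3 of the first patients suffer a grade 3 or 4 immune related toxicity of interest" within 28 days of the first nivolumab dose, the study stops.
- **Phase Ib cohort, counting immune mediated events of interest.** "If, at any time during accrual to the phase 1 b portion, 6 patients or more have a grade 3 or 4" event, the study is paused and then modified or discontinued in consultation with the site principal investigators and regulators.

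The cohort is limited: "Up to 10 total patients will be treated and observed for toxicity for 28 days from the first dose of Nivolumab in the phase 1b". The gate to phase II is "If 5 or fewer patients experience grade 3 or 4 immune mediated toxicity of interest (see 5.2.1) during the toxicity window, then the study will" proceed. The reason given for the threshold of 6 is that the exact 95% interval for 6/10 (26% to 88%) lies above 25%, which the plan takes as a sign of too much immune mediated toxicity.

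After that, the only study-level rule is response futility: stop at 2 or fewer responders of the first 12 (Section 11.2). In the same section, the DLT analysis is a phase Ib item ("Type, grade and attribution will be described by body system in the first 10 DLT evaluable patients"), and safety over the whole trial is a descriptive secondary endpoint. Section 12.0 moves DSMC meetings from monthly to quarterly in phase II and states no numerical trigger.

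The Methodology row of the synopsis carries the same phase Ib limit ("If, at any time during accrual to the phase1 b portion, 6 patients or more have a grade 3 or 4 immune mediated event of" this kind). The Statistical Methodology row omits it: "If, at any time during accrual, 6 patients or more have a grade 3 or 4 immune mediated event of interest".

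**The concern.** The plan names a level of evidence at which immune toxicity is judged excessive, then stops applying it when 13 of the 23 evaluable patients (23 - 10) are still to be treated. The gate into phase II is permissive, since it passes a cohort with half its patients having a DLT. A regimen that passed on a favorable or borderline first ten could therefore meet the plan's own criterion during phase II, and no rule would require anyone to pause and consult.

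What is at stake is a pre-agreed point of action for the study as a whole. Whether individual patients are managed or monitored is not in question.

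**Working it through.** **Inputs.** From Section 11.1: stop at 2 or more of 3; pause at 6 or more during phase Ib (10 patients); criterion that the two-sided exact 95% interval lies above 25%; total 23 evaluable. The documents give no true DLT rate, so a constant rate p is assumed and varied from 25% to 60%.

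**Step 1: reproduce the plan's figure.** The exact (Clopper-Pearson) limits for x events in n patients are

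- lower = 2.5% quantile of Beta(x, n - x + 1)
- upper = 97.5% quantile of Beta(x + 1, n - x)

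For 6/10 this gives 26.2% to 87.8%, which agrees with the stated 26% to 88%. For 5/10 it gives 18.7% to 81.3%. So 6 is the smallest count of 10 that meets the criterion, and 5/10 passes.

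**Step 2: carry the criterion past patient 10.** For each n, take the smallest x whose lower limit exceeds 25%. In each band the limit is tightest at the largest n. One event fewer comes closest to qualifying at the smallest n.

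| Evaluable patients | Smallest count | Lower limit at largest n | One fewer, at smallest n |
|---|---|---|---|
| 11-13 | 7 | 7/13: 25.1% | 6/11: 23.4% |
| 14-15 | 8 | 8/15: 26.6% | 7/14: 23.0% |
| 16-18 | 9 | 9/18: 26.0% | 8/16: 24.7% |
| 19-21 | 10 | 10/21: 25.7% | 9/19: 24.5% |
| 22-23 | 11 | 11/23: 26.8% | 10/22: 24.4% |

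A study that opens phase II at 5/10 meets the criterion at patient 12 if patients 11 and 12 both have a DLT (7/12, lower limit 27.7%). It meets it by patient 23 with 6 DLTs in the last 13 (11/23).

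**Step 3: chance of passing phase Ib.** With a DLTs in the first 3 patients,

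P(pass) = sum over a = 0, 1 of P(a of 3) x P(at most 5 - a of 7).

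At p = 50%: 0.125 x 0.9375 + 0.375 x 0.7734 = 0.407.

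**Step 4: chance of meeting the criterion in patients 11 to 23.** Start from the distribution of the 10-patient count among trials that passed. Add one patient at a time and remove the paths that reach the Step 2 count. The unconditional chance is P(pass) times the conditional chance; at 50%, 0.407 x 0.548 = 0.223.

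| True DLT rate | Pass phase Ib | Criterion met in 11-23, given passage | Unconditional | Mean patients not treated, given passage |
|---|---|---|---|---|
| 25% | 84% | 1.9% | 1.6% | 0.1 |
| 40% | 60% | 24% | 14% | 1.5 |
| 50% | 41% | 55% | 22% | 3.5 |
| 60% | 22% | 82% | 18% | 6.0 |

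The last column treats every pause as ending accrual, with each patient's 28-day window complete before the next enrolls. It is therefore an upper bound under this model. None of the figures allow for the futility stop at 12. Under Section 11.1 as written, the chance of a rule-triggered toxicity pause in patients 11 to 23 is zero at every rate.

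**The case against.** The strongest reply is that this is a legitimate design choice. DLT is a phase Ib endpoint, later safety is descriptive, and the plan justifies one examination at 10 patients. A boundary checked after each later patient is an extension of that reasoning, not something the plan implies. The phase Ib rules also do most of the work: they already stop or pause 40%, 59% and 78% of trials at true rates of 40%, 50% and 60%. That is why the unconditional gain is only 14% to 22% at those rates. Both points stand, and they are why this is an improvement and not an error.

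A reader might infer that patients 11 to 23 are treated without safety oversight. The documents do not support that. The hold and discontinue rules of Section 5.2, SAE reporting under 8.5, toxicity calls at least weekly in the first 12 weeks (6.2.3), DSMC review (12.0) and termination by the institution or regulators (5.8.8) all remain. Only a numerical study-level trigger is absent.

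A reader might also infer from the synopsis statistics row that a rival rule applies, pausing at 6 events at any point up to 23 patients. That does not hold either. The sentence stands in the phase Ib paragraph, follows the statement that 10 patients are observed, and leads into the decision to open phase II and the 10-patient justification. A count that decides entry to phase II cannot sensibly also run through it. It is a dropped qualifier. Nor does the plan call a 25% DLT rate acceptable; it says only that an interval above 25% is too great.

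One limitation remains. The cumulative count pools 3 sequentially treated patients with later ones on the interspersed schedule. The plan already pools them in its 10-patient count, so the extension adds no new assumption there.

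**Conclusion.** The point holds as a cheap improvement: no pre-specified study-level toxicity boundary exists after patient 10, although the plan's own criterion can be met after that. At a true DLT rate of 50%, about four trials in ten reach phase II, and just over half of those would go on to meet the criterion; that is 22% of all trials. At 25% the criterion would rarely be met (1.9% given passage).

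The intervals and boundary counts depend only on the plan's criterion. The probabilities rest on a constant DLT rate across both schedules, independent patients and a check after each patient from 11 to 23, with no reporting lag.

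**What to change.** - **Section 11.1.** Extend the existing pause-and-consult rule to all accrual, applied to the cumulative number of DLT-evaluable patients: pause at 7 or more DLTs in 11-13 patients, 8 in 14-15, 9 in 16-18, 10 in 19-21 and 11 in 22-23. Keep the present DLT definition and 28-day window. State that the Coordinating Center keeps the tally.
- **Section 8.8.** Keep the reference to 11.1, which would then cover the whole trial.
- **Synopsis, Statistical Methodology.** As a wording correction only, restore the phase Ib qualifier to the 6-patient sentence so that it matches the Methodology row and Section 11.1, and add the later boundaries.

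**Cost.** Amendment text and a running count from adverse events already collected; no extra patients or procedures. There is one real operational demand: DLTs must be attributed promptly in phase II, with reversible IL-2 events excluded, at a stage when the biweekly cross-site calls have ended and routine safety reports are quarterly. The statistical price is about a 2% chance, given entry to phase II, of an unneeded pause if the true rate is 25%. The action would be a pause for consultation, not automatic termination.

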#### **Study Endpoints**

##### **Phase Ib portion:**

Primary Endpoint: To establish that the combination of High Dose Interlukin-2 and Nivolumab is safe and tolerable by monitoring 10 patients for immune mediated grade 3/4 events of interest for 28 days from the first dose of Nivolumab.

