## 5.0 TREATMENT PLAN

### 5.1 Treatment Dosage and Administration

Protocol treatment must start within 14 business days of enrollment to the study. The interleukin-2 (Proleukin) and Nivolumab (Opdivo) will be stored and prepared as described in the approved labels.

- 5.1.1 Therapy will start with high dose interleukin-2 (HD IL2) on week1 (day 1-5) and again on week 3 (day 1-5). Nivolumab will start on week 2 (optimally day 1 but can be given up to 3 weeks after IL-2 start but NOT be on the same week as any HD IL2 cycle) and continue every 4 weeks for up to 48 weeks on study unless one of the dose delay or stopping rules apply.
- 5.1.2 HD IL-2 will be administered in standard fashion at a fixed dose of 600,000 IU/kg/dose every 8 hours for a total of up to 14 doses (considered as one cycle) over 5 consecutive days (D1-D5), followed by a 9-day break and then another cycle at the same dose over another 5 consecutive days (D15-D19). Each HD IL-2 course consists of two cycles of up to 14 doses each separated by 9 days of rest.

Monitoring, supportive care measures for HD IL2 will be per institutional guidelines. The standard current guidelines for HD IL-2 administration based on Schwartzenruber et al. have proven to be safe at the participating institutions in the study over the years and will be used for this protocol.

Pre-medications and concurrent medications: Per institutional guidelines at each site usually include anti-emetics, anti-histamines, antipyretics/anti-inflammatory agents, anti-motility/anti-diarrheal agents, proton pump inhibitors, vasopressors as needed, medications for rigors as needed, hydration including boluses and maintenance fluids. It is recommended but not mandated that subjects be given anti-emetics for as needed (prn) use after each IL-2 therapy week to treat residual nausea. Furosemide (a loop diuretic) may also be given per treating investigator's discretion following each IL2 week. Please see IL-2 guidance document for more details.

Subjects will undergo placement of a central venous catheter before each course or cycle of therapy per institutional preferences.

NOTE: If the treating investigator determines another course of HD IL-2 beyond the 2 cycles after week 12 of protocol therapy specified in the protocol are in the

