subject's best interests, it is permissible and will be recorded in follow-up. If so, nivolumab should be held during IL2 weeks. No protocol specified assessments are required for the repeat course.

- 5.1.3 Nivolumab will be administered intravenously at a standard dose of 480 mg/dose every 4 weeks starting on week 2 (ideally day 1 of week 2 but can be given up to 3 weeks after IL-2 start but NOT be on the same week as any HD IL2 cycle) and continued as long as clinical benefit continues as determined by the treating investigator for up to 48 weeks on study.
- 5.1.4. The first 3 patients will be treated with sequential (rather than interspersed) treatment. They will receive 2 cycles of HD-IL2 given in standard fashion (two 5-day cycles one week apart) followed by nivolumab starting the week after the second IL-2 cycle and continuing every 4 weeks as per standard nivolumab dosing.

We will perform a safety analysis after the first 3 patients are treated and if 2/3 patients suffer a grade 3 or 4 immune related toxicity, the study will stop. The 4th patient will not be enrolled until after the analysis of the 3 patient cohort is complete and submitted to the regulatory bodies

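### The phase Ib safety gate pools 3 sequential and 7 later patients, so after a 0-of-3 lead-in, 5 DLTs among the later 7 still open phase II

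*Combined protocol and SAP*

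**What the plan says.** - **Lead-in (5.1.4, 11.1).** The first 3 patients receive both IL-2 cycles, "followed by nivolumab starting the week after the second IL-2 cycle". Two or more DLTs among them stop the study.
- **Patients 4 to 10 (11.1).** Nivolumab is given at "480 mg/dose over 60 minutes every 28 days, starting 1 to 3 weeks after the start date of the first cycle of IL2". Section 5.1.1 targets week 2 and adds that it "can be given up to 3 weeks after IL-2 start but NOT be on the same week as any HD IL2 cycle". With IL-2 on days 1-5 and 15-19, that leaves week 2 or about day 22.
- **Endpoint (Study Endpoints, Phase Ib).** It consists of "monitoring 10 patients for immune mediated grade 3/4 events of interest for 28 days from the first dose of Nivolumab".
- **Gate (Synopsis, 11.1).** Six or more events lead to a pause and consultation. The go-ahead reads "If ≤ 5 of the 10 patients have a grade 3 or 4 immune mediated event of interest", after which phase II opens. The reason given in 11.1 is that "if 6 patients or more are found to have a DLT then the 95% exact binomial confidence interval (26% - 88%) will be > 25" (per cent), which the plan takes to show that toxicity is too great.
- **Other stopping rules (8.8).** "Please refer to Section 11.1" is the whole section.
- **Reporting (11.2).** "DLT count and proportion will be reported" for the first 10 DLT-evaluable patients, with no split by schedule.

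**The concern.** The protocol treats the two schedules as different enough to try the sequential one first, to give it its own stopping rule, and to hold back patient 4 until that cohort has been analysed. A lead-in patient's 28-day DLT window opens after protocol IL-2 has ended. A patient who starts nivolumab in week 2 has the scheduled second IL-2 cycle inside the window. The numerical gate to phase II nevertheless adds the two groups together, and nothing is specified for the later 7 alone.

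A clean lead-in therefore raises the number of DLTs tolerated among the later patients: 5 of 7 after 0 of 3, but 4 of 7 after 1 of 3. This is the last numerical safety gate, since 11.1 confines the 6-patient pause to phase Ib accrual. If it opens, up to 13 more evaluable patients (23 - 10) are treated with week 2 as the target start.

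**Working it through.** **Inputs from the documents.** Lead-in of 3, passing with 0 or 1 DLT; 7 further patients; pause at 6 or more of 10; criterion of an exact two-sided 95% interval above 25%; IL-2 cycle 2 on days 15-19; DLT window of 28 days from the first nivolumab dose.

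**Assumptions.** The documents give no DLT rate for the combination. I take a sequential rate s of 0% to 25% and an interspersed rate p of 25% to 70%. Except in step 6, all 7 later patients are assumed to start nivolumab before cycle 2.

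**1. The plan's own figure.** The Clopper-Pearson limits for x of n are the 2.5% quantile of Beta(x, n-x+1) and the 97.5% quantile of Beta(x+1, n-x).
- 6/10: 26.2%-87.8%, which agrees with the stated 26%-88%.
- 5/10: 18.7%-81.3%. Six is therefore the smallest count of 10 that meets the criterion.

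**2. The same criterion extended to 7.**
- 4/7: 18.4%-90.1%, not met.
- 5/7: 29.0%-96.3%, met.
- 6/7: 42.1%-99.6%, met.

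**3. What the pooled rule does.**
- Lead-in 0/3: 0 + 5 = 5 of 10, proceed. A pause needs 6 of 7 (86%).
- Lead-in 1/3: 1 + 5 = 6 of 10, pause. At most 4 of 7 can proceed, and 4/7 does not meet the criterion.

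The pooled rule and a 5-of-7 rule thus differ in exactly one outcome: 0 of 3 followed by exactly 5 of 7.

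**4. Chance of a pause, given that the lead-in passed.** With X ~ Binomial(7, p):
- P(0 of 3 | passed) = (1-s)^3 / [(1-s)^3 + 3s(1-s)^2] = (1-s)/(1+2s). This is 1 at s = 0 and 0.75/1.5 = 0.5 at s = 25%.
- Pooled rule: P(0 of 3 | passed) × P(X≥6) + P(1 of 3 | passed) × P(X≥5).
- With a 5-of-7 rule added: P(X≥5).

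| p | P(X≥6) | P(X≥5) | Pooled, s = 0 | Pooled, s = 25% | With added rule |
|---|---|---|---|---|---|
| 25% | 0.0013 | 0.0129 | 0.1% | 0.7% | 1.3% |
| 50% | 0.0625 | 0.2266 | 6% | 14% | 23% |
| 60% | 0.1586 | 0.4199 | 16% | 29% | 42% |
| 70% | 0.3294 | 0.6471 | 33% | 49% | 65% |

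Example, p = 60% and s = 25%: 0.5 × 0.1586 + 0.5 × 0.4199 = 0.289.

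**5. If schedule makes no difference (s = p).** The gain is P(0 of 3 | passed) × P(X = 5).
- 50%: 0.250 × 0.1641 = 4.1 points.
- 60%: 0.182 × 0.2613 = 4.8 points.
- 70%: 0.125 × 0.3177 = 4.0 points.

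**6. Fewer than 7 week-2 starters.** The smallest counts with a lower limit above 25% are 5/6 (35.9%), 4/5 (28.4%), 4/4 (39.8%) and 3/3 (29.2%). One fewer fails each time: 4/6 (22.3%), 3/5 (14.7%), 3/4 (19.4%), 2/3 (9.4%). With 2 patients the criterion cannot be met (2/2: 15.8%).

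**The case against.** **The criterion is written for 10 patients.** This stands. A reader might infer that the plan breaks its own rule at 5 of 7. It does not: 11.1 states the criterion for 10 patients and for the regimen as a whole. Applying it to the 7 extends the plan's reasoning; it does not expose a contradiction in the text.

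**The later patients need not be interspersed.** This also stands. A reader might infer that patients 4 to 10 and everyone in phase II receive the interspersed schedule. A day-22 start is allowed and matches the lead-in timing, which makes pooling more defensible than it first looks. Week 2 is still the stated target, and no boundary covers those who follow it.

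**The affected outcome is narrow.** Only 0/3 with exactly 5/7 changes. The large gains need a marked schedule effect, for which the documents give no evidence; with equal rates the gain is 4-5 points. The nearest figure in the documents is 19% grade 3 or 4 treatment-related events on nivolumab alone (section 1.2), which is not a DLT rate for the combination. On the other hand, 0 of 3 is the likeliest passing result whenever the sequential rate is below 25%, because (1-s)/(1+2s) then exceeds one half.

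**Other safeguards exist.** Section 5.2 holds IL-2 cycle 2 until immune-mediated toxicity is grade 1 or better and steroids are at a low dose, so the window need not contain cycle 2 at all. The Synopsis has DLTs reported as they occur, and section 12 provides monthly committee review and biweekly calls. These protect individual patients and allow discretionary action. None sets a number for the later 7, and the written instruction at 5 of 10 is to continue. The DLT definition also leaves out reversible events that might occur during high-dose IL-2, so the counts concern immune-mediated events.

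**Conclusion.** The point holds as a gap in the gate, not as an error or an internal contradiction. After a 0-of-3 lead-in, 5 DLTs among the later 7 (29.0%-96.3%) open phase II, although the plan's 25% criterion, carried over to those 7, would call for a pause. After 1 of 3 the present rule already pauses at 5 of 7.

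If all 7 start before cycle 2 and the sequential rate is 0%-25%, an added rule raises the chance of a pause from 6%-14% to 23% at an interspersed rate of 50%, from 16%-29% to 42% at 60%, and from 33%-49% to 65% at 70%. If the schedules share one of those rates, it adds 4-5 points. These rates are assumptions, and how many patients will start on day 22 is unknown.

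A reader might also infer that un-pooling would make the gate strong. It would not: at a 60% rate the added rule still misses 58% of the time, because 7 patients carry little information. The change is worth making because it is cheap and bears on patient safety.

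**What to change.** In 11.1 keep the 2-of-3 and 6-of-10 rules and add:

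> Pause also if 5 or more of the patients enrolled 4th to 10th who received their first nivolumab dose before day 15, or before IL-2 cycle 2 if that cycle was delayed, have a DLT; a patient whose cycle 2 was held or never given after that dose counts. If phase Ib closes with fewer than 7 such patients, pause at 5 of 6, 4 of 5, 4 of 4 or 3 of 3; with 1 or 2 such patients only the 6-of-10 rule applies.

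In 11.2 report the DLT count and proportion separately for patients first dosed with nivolumab before and after cycle 2, using the same definition. The Simon boundaries stay as they are.

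**Cost.** One added rule and one split row, built from dosing dates that the trial needs anyway, and no extra patients. At a true interspersed rate of 25%, the chance of an unneeded pause rises from at most 0.7% to 1.3% (sequential rate 0%-25%). A pause leads to consultation on changing or ending the protocol, not to automatic closure.
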